### 1.3. Schedule of Activities

**Table 1 Schedule of Activities**

Visit Name	Screening	Treatment Period				Follow-Up		Notes
		Baseline	Weeks 1, 2, 3, etc.	Early Termination*	EOT/Delivery	F1	F2 (EOS)	
Day/Week (Window)	Day -10 to -1	0*	Every 7 Days (±1 Day) Until Delivery		Day of Delivery (+2 Days)	Phone Call: 14 Days after Delivery (±3 Days)	Clinic Visit: 28 Days after Delivery (±3 Days)	
*Participants who early terminate from study drug should still continue with weekly visits through delivery, F1, and F2.
 
Some visits may be conducted as a home health or remote visit at the discretion of the investigator upon approval by the sponsor or designee and in accordance with local and regional regulations.
 
*See Section 8.1.8 for further details on timing of baseline visit.

Administrative Procedures								
Informed consent	X							
Eligibility Procedures								
Inclusion/exclusion criteria	X	X						
Demography	X							
Prior/concomitant treatment	X	X	X	X	X	X	X	
Medical history	X	X						Includes menstrual and obstetric history
Estimated gestational age assessment	X							Confirmation of eligibility based upon estimated gestational age required before randomization: CRL from early ultrasound or head circumference on ultrasound if CRL is >84 mm.

Visit Name	Screening	Treatment Period				Follow-Up		Notes
		Baseline	Weeks 1, 2, 3, etc.	Early Termination*	EOT/Delivery	F1	F2 (EOS)	
Day/Week (Window)	Day -10 to -1	0*	Every 7 Days (±1 Day) Until Delivery		Day of Delivery (+2 Days)	Phone Call: 14 Days after Delivery (±3 Days)	Clinic Visit: 28 Days after Delivery (±3 Days)	*Participants who early terminate from study drug should still continue with weekly visits through delivery, F1, and F2.  Some visits may be conducted as a home health or remote visit at the discretion of the investigator upon approval by the sponsor or designee and in accordance with local and regional regulations. *See Section 8.1.8 for further details on timing of baseline visit.
Hepatitis and HIV screen, TSH	X							If HIV results are documented as negative from the current pregnancy in a participant deemed to be low risk by the investigator, HIV at screening visit may be waived.
Dosing Procedures								
Randomization		X						
Study drug dispensing		X	X					As needed
Study drug collection/reconciliation			X	X	X			As needed
Efficacy Procedures								

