#### **Part 1: Proof of Concept, Safety/Tolerability, Dose Ranging, Pharmacokinetics, and Interim Analysis**

After a screening period of up to 10 days, eligible participants diagnosed with ICP with screening sBA  $\geq 10$   $\mu\text{mol/L}$  will be randomized with stratification (based on background use of UDCA or not, on gestational age [ $<32$  weeks or  $\geq 32$  weeks] at randomization, and presence/absence of gestational diabetes) in a 2-arm (1:1), open-label fashion to receive volixibat 20 mg BID or volixibat 80 mg BID.

Study-drug dosing will begin on Day 0 and continue until end of the treatment period, defined as the day of delivery. Study visits to assess safety, plasma concentrations of volixibat, pharmacodynamics, and efficacy will be conducted from baseline (Day 0) until delivery at time points specified in the schedule of activities (SoA; [Table 1](#)). Because alternative measures may be implemented when necessary for public health or other emergency situations, and when sufficient to help ensure the safety of study participants, some visits may be conducted as a home health or remote visit at the discretion of the investigator upon approval by the sponsor or designee and in accordance with local and regional regulations ([Appendix 11](#); [FDA 2020](#)). Participants will also enter ItchRO assessments into an electronic diary (eDiary) once daily (QD). Use of limited rescue therapies for ICP will be permitted for participants who meet protocol-specified criteria.

Interim analyses are detailed in [Section 10.4.4](#).

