### **Part 1: Proof of Concept, Dose Ranging, Pharmacokinetics, and Interim Analysis**

After a screening period of up to 10 days, eligible participants will be identified for one of two cohorts, defined as follows:

- Primary cohort: Participants with ICP with a screening sBA level  $\geq 20$   $\mu\text{mol/L}$  will be randomized with stratification (based on gestational age [ $<32$  weeks or  $\geq 32$  weeks] at randomization, presence/absence of gestational diabetes, and highest sBA before randomization [ $<40$   $\mu\text{mol/L}$ ,  $\geq 40$   $\mu\text{mol/L}$  to  $<100$   $\mu\text{mol/L}$ , or  $\geq 100$   $\mu\text{mol/L}$ ]) in a 3-arm (1:1:1), double-blind fashion to receive volixibat 20 mg BID, volixibat 80 mg BID, or placebo.
- Supplemental cohort: Up to 30 participants with ICP with screening sBA level from  $\geq 15$  to  $<20$   $\mu\text{mol/L}$  will be randomized (based on gestational age at randomization and presence/absence of gestational diabetes) in a 2-arm (1:1), open-label fashion to receive volixibat 20 mg BID or volixibat 80 mg BID.

Study treatment dosing will begin on Day 1 and continue until end of the study treatment period, defined as the day of delivery. Study visits to assess safety, plasma concentrations of volixibat, pharmacodynamics, and efficacy will be conducted weekly from baseline until

delivery. Because alternative measures may be implemented when necessary for public health or other emergency situations, and when sufficient to help ensure the safety of study participants, some visits may be conducted as a home health or remote visit at the discretion of the investigator upon approval by the medical monitor or designee and in accordance with local and regional regulations (see Protocol Appendix 10). Participants will also enter ItchRO assessments into an electronic diary (eDiary) once daily. Use of limited rescue therapies for ICP will be permitted for participants who meet protocol-specified criteria.

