##### **4.2.1. Duration of Exposure to Study Drug**

Total duration of exposure to study drug will be defined as last dosing date minus first dosing date plus 1, regardless of any temporary interruptions in study drug administration except for protocol-specified dose holds and/or dose reductions, and will be expressed in weeks using up to 1 decimal place (eg, 4.5 weeks). If the last study drug dosing date is missing, the latest date among the study drug end date, clinical visit date, laboratory sample collection date, and vital signs assessment date will be used.

The total duration of exposure to study drug will be summarized using descriptive statistics and using the number (ie, cumulative counts) and percentage of participants exposed through the following time periods: 1 day, 3 weeks, 6 weeks, 9 weeks, 12 weeks, 15 weeks, 18 weeks, and >18 weeks. Summaries will be provided by treatment group for the Safety Analysis Set.

No formal statistical testing is planned.

A listing of exposure to the study drug will be provided.

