#### **7.1.5. Treatment-Emergent Adverse Events**

##### **7.1.5.1. Definition of Treatment-Emergent Adverse Events**

Maternal treatment-emergent adverse events (TEAEs) are defined as AEs that start or deteriorate on or after the first dose of study medication and no later than 7 days following the last dose of study medication. For any participants (i.e., mothers) who die during the study and the date of death is between the date of the first dose of study medication and the date of study discontinuation (as entered by the site), inclusive, all AEs (including those

resulting in death) that occur during the study will be considered as TEAEs irrespective of the last dose and will be included in the TEAE summaries. All summaries of AEs will be based on TEAEs unless specified otherwise.

For newborns, all reported AEs will be considered TEAEs for the purpose of summaries.

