### **7.2. Laboratory Evaluations**

Laboratory data collected during the study will be analyzed and summarized using both quantitative and qualitative methods. Summaries of laboratory data will be provided for the Safety Analysis Set and will include data collected up to the last dose of study drug plus 7 days for participants who have permanently discontinued study drug, or all available data at the time of the database snapshot for participants who were ongoing at the time of an interim analysis. The analysis will be based on values reported in conventional units. When values are below the LOQ, they will be listed as such, and the closest imputed value will be used for the purpose of calculating summary statistics as specified in [Section 3.7](#). Hemolyzed test results will not be included in the analysis, but they will be listed in by-participant laboratory listings.

A by-participant listing for laboratory test results will be provided by participant ID number and time point in chronological order for hematology, serum chemistry, and urinalysis separately.

No formal statistical testing is planned.

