### 13. APPENDIX 1 SCHEDULE OF ACTIVITIES

**Table 7 Schedule of Activities**

Visit Name	Screening	Treatment Period				Follow-Up		Notes
		Baseline	Week 1, 2, 3, etc.	Early Term*	EOT/Delivery	F1	F2 (EOS)	
Day/Week (Window)	Day -10 to -1	0*	Every 7 Days (±1 Day) Until Delivery		Day of Delivery (+2 Days)	Phone Call: 14 Days after Delivery (±2 Days)	Clinic Visit: 28 Days after Delivery (±3 Days)	*Participants who early terminate from study drug should still continue with weekly visits through delivery, F1, and F2.  Some visits may be conducted as a home health or remote visit at the discretion of the investigator upon approval by the medical monitor or designee and in accordance with local and regional regulations.  *Regardless of date of screening visit, baseline visit must occur no later than 35 weeks and 0 days gestational age.
Administrative Procedures								
Informed consent	X							
Eligibility Procedures								
Inclusion/exclusion criteria	X	X						
Demography	X							
Prior/concomitant treatment	X	X	X	X	X	X	X	
Medical history	X	X						Includes menstrual and obstetric history
Estimated gestational age assessment	X							Confirmation of eligibility based upon estimated gestational age required before randomization: CRL from early ultrasound or head circumference on ultrasound if CRL is >84 mm.
Hepatitis and HIV screen, TSH	X							
Dosing Procedures								
Randomization		X						
Study treatment dispensing		X	X					As needed
Study treatment collection/reconciliation			X	X	X			As needed

Visit Name	Screening	Treatment Period				Follow-Up		Notes
		Baseline	Week 1, 2, 3, etc.	Early Term*	EOT/Delivery	F1	F2 (EOS)	
Day/Week (Window)	Day -10 to -1	0*	Every 7 Days (±1 Day) Until Delivery		Day of Delivery (+2 Days)	Phone Call: 14 Days after Delivery (±2 Days)	Clinic Visit: 28 Days after Delivery (±3 Days)	
*Participants who early terminate from study drug should still continue with weekly visits through delivery, F1, and F2.
 
Some visits may be conducted as a home health or remote visit at the discretion of the investigator upon approval by the medical monitor or designee and in accordance with local and regional regulations.
 
*Regardless of date of screening visit, baseline visit must occur no later than 35 weeks and 0 days gestational age.

Efficacy Procedures								

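### SAP 4.2.1 imputes a missing last-dose date as the latest contact date with no cap, so a participant who is off drug and attends F2 is treated as dosed until 25 to 31 days after delivery

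*SAP*

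**What the plan says.** SAP 4.2.1 defines exposure as "last dosing date minus first dosing date plus 1". For participants without a last dosing date, the rule is that "the latest date among the study drug end date, clinical visit date, laboratory sample collection date, and vital signs assessment date will be used". SAP 3.6.1 points to 4.2.1 as the place where imputation of a missing last dosing date is described, and the SAP gives no other rule for it.

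On the end of dosing, SAP 1.2 says that treatment is to "continue until end of the study treatment period, defined as the day of delivery"; Protocol 4.1 says the same. On follow-up, Protocol Table 1 states: "Participants who early terminate from study drug should still continue with weekly visits through delivery, F1, and F2". In both schedules of activities F2 is a clinic visit 28 days after delivery with a window of 3 days either side, and it includes haematology, chemistry, coagulation, weight and vital signs.

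Four other definitions depend on the last-dose date:

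- Maternal treatment-emergent events (SAP 7.1.5.1) must start or worsen "no later than 7 days following the last dose of study medication".
- Laboratory summaries (SAP 7.2) take "data collected up to the last dose of study drug plus 7 days for participants who have permanently discontinued study drug".
- The adherence denominator (SAP 4.2.2) is twice the duration of exposure.
- Concomitant medications (SAP 4.3.2) exclude those started after the last dosing date.

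**The concern.** The rule takes the maximum of four dates, and three of them go on accruing after drug has stopped. In this trial the last scheduled one falls about four weeks after the latest day on which any dose could have been taken. Because the later date wins, a recorded study drug end date does not protect against this.

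What is at stake is the accuracy of the safety description. Maternal adverse events are collected to F2 or beyond (Protocol 8.3.1), so postpartum events exist that could be labelled treatment-emergent. F2 laboratory values would enter the on-treatment summaries, although the protocol's background section says that the signs of the disease resolve within a few weeks of delivery. The error is largest for participants who stopped early, who matter most for tolerability.

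**Working it through.** The plan gives no figure to reproduce. The check is date arithmetic in SAP study days, with the first dose on Day 1.

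**Inputs.** F2 falls 28 days after delivery, range 25 to 31 (both schedules). Exposure = last dose − first dose + 1 (SAP 4.2.1). Maternal treatment-emergent cut-off = last dose + 7 days (SAP 7.1.5.1). Laboratory cut-off = last dose + 7 days (SAP 7.2). Adherence = doses taken / (2 × exposure in days) (SAP 4.2.2). Delivery on Day 22 is my assumption; it is the nominal Week 3 day (3 × 7 + 1).

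**Case A: dosed to delivery on Day 22, last-dose date missing, attends F2.**

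- Imputed last dose: 22 + 28 = Day 50 (22 + 25 = 47; 22 + 31 = 53).
- Exposure: 50 days (47-53) against a true 22. Ratio 50/22 = 2.27. In weeks, 7.1 (6.7-7.6) against 3.1, which moves her past the 6-week exposure category.
- Treatment-emergent window: ends on 50 + 7 = Day 57 against 22 + 7 = Day 29. That is 35 days after delivery (32-38) instead of 7.
- Adherence with every dose taken: 44 / (2 × 50) = 44% against 44 / (2 × 22) = 100%. She drops from the top adherence category to the one below 80%.
- Laboratory data: F2 on Days 47-53 lies inside the extended cut-off. It coincides with the Week 7 window of SAP Table 2 (7 × 7 − 2 = 47 to 7 × 7 + 4 = 53), so postpartum values would be summarised as Week 7 results.

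**Case B: last dose on Day 8, delivery on Day 22, otherwise the same.**

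- Exposure: 50 days against 8, ratio 50/8 = 6.25.
- Treatment-emergent window: ends on Day 57 against 8 + 7 = Day 15.
- Adherence with every dose taken up to Day 8: 16 / 100 = 16%.

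**Case C: last dose on Day 8, delivery on Day 36.**

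- Imputed last dose: 36 + 28 = Day 64, so exposure is 64 days against 8.
- Treatment-emergent window: ends on Day 71, which is 63 days after drug was stopped.

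**Sensitivity to the assumed delivery day, dosed to delivery.** A true exposure of 15 days becomes 43 (ratio 2.9), and 43 days becomes 71 (ratio 1.7). The absolute excess is always 28 days (25-31); only the ratio changes.

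**What does not move.** Time at risk for exposure-adjusted incidence rates ends at event onset or study completion/early termination (SAP 7.1.7), so it does not use the last-dose date. All newborn events count as treatment-emergent regardless (SAP 7.1.5.1). The analysis sets in SAP Table 1 and the efficacy endpoints do not use the last-dose date.

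**The case against.** **Missing dates may be rare.** Drug collection and reconciliation are scheduled at the weekly, Early Termination and Delivery visits (Protocol Table 1). Accountability is at capsule level (Protocol 6.6). The stop date must be recorded in source documents for participants who withdraw (Protocol 7.2). Delivery at another hospital is provided for (Protocol 8.1.13), and continued weekly visits give sites more chances to obtain the date. This stands: the documents do not support a claim that the rule will be used often.

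**The rule has a legitimate use.** The SAP also serves an interim analysis and has a disposition category for participants still taking drug. For them, the latest contact is a sensible stand-in for a last dose that has not yet happened. This stands too, but it does not justify the rule for participants who have finished or stopped treatment.

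**Over-inclusion is conservative.** The SAP counts events with missing causality as related (7.1.3) and most events with a missing onset date as treatment-emergent (7.1.5.2), and it lists all events with a flag. That is a fair argument for adverse events. It does not cover overstated exposure, understated adherence, or laboratory values from postpartum recovery reported as on-treatment. SAP 4.2.2 itself describes adherence as relating to the actual on-treatment period, which a date after delivery contradicts.

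**The dose-reduction clause.** A reader might infer that the exception in 4.2.1 for protocol-specified dose holds and reductions removes reduced-dose days from exposure. The formula has no subtraction term, and the clause is ambiguous. It merits at most a wording clarification.

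**Conclusion.** The point holds. Whenever the rule is applied to a participant who is off drug and attends F2, it returns a last-dose date on which dosing was impossible by design. Exposure is overstated by 28 days (25-31) for someone dosed to delivery, and by more for an early stopper. The maternal treatment-emergent, laboratory, adherence and concomitant-medication derivations inherit the error.

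The size rests on three things: the last-dose date is missing (frequency not given), the participant attends F2, and SAP 3.6.1 makes 4.2.1 the general rule, since the later sections do not restate it. A participant who withdraws before F2 gets her last contact date, which may still fall after her last dose.

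A reader might infer that the trial's safety conclusions or its efficacy results are compromised. The documents do not support that. The figures are per-participant examples, the affected summaries are descriptive, and the efficacy analyses, newborn events and time at risk for incidence rates are unchanged. This is a stated rule that gives a wrong answer in a definable set of participants. It should be corrected, but it does not threaten the trial's main inference.

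**What to change.** Amend SAP 4.2.1 to separate two groups.

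1. **Participants off treatment.** Use the recorded study drug end date if there is one. Otherwise use the last on-treatment visit or drug-accountability date, capped at the earlier of the Early Termination visit and delivery. Never use F1 or F2.
2. **Participants still on drug at an interim data cut.** Keep the latest-contact rule.

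Reporting the number of imputed last-dose dates by arm would show how much the rule matters.

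Do not add a step that subtracts days without drug. SAP 4.2.1 counts duration regardless of temporary interruptions, and adherence uses that duration as its denominator. In an assumed example of 22 days with no drug on 6 and 32 doses taken, the SAP gives 32/44 = 73%; after subtraction it would be 32/32 = 100%, which hides the missed days. The drug-accountability totals also do not show which days were missed. If the exception for dose holds and reductions is kept, state what it means in one clause.

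The cost is one sentence of SAP text and one derivation, with no new data. It should be done before database lock.

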##### **4.2.2. Adherence to Study Drug**

The total number of tablets administered will be summarized using descriptive statistics.

The presumed total number of doses tablets administered to a participant will be determined by the data collected within IXRS for drug accountability using the following formula:

$$\text{Total Number of Doses Administered} = \left( \sum \text{No. of Doses Dispensed} \right) - \left( \sum \text{No. of Doses Returned} \right)$$

The level of on-treatment adherence to the study drug regimen will be determined by the total amount of study drug administered relative to the total amount of study drug expected to be administered during a participant's actual on-treatment period based on the study drug regimen.

The level of on-treatment adherence will be expressed as a percentage using the following formula:

$$\text{On-Treatment Adherence (\%)} = \left( \frac{\text{Total Amount of Study Drug Administered}}{\text{Study Drug Expected to be Administered on Treatment}} \right) \times 100$$

Where, the amount of study drug expected to be administered on treatment will be derived as 2 x Duration of Exposure to Study Drug, which is defined in [Section 4.2.1](#). Descriptive statistics for the level of on-treatment adherence with the number and percentage of participants belonging to adherence categories (eg, <80%, ≥80 to <90%, ≥90%) will be provided by treatment group for the Safety Analysis Set.

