## 6. TREATMENTS

### 6.1. Investigational Product

Volixibat in capsules at doses of 20 mg and 80 mg and matched placebo will be supplied (in a blinded fashion for Part 2) for oral dosing BID. As much as possible, the morning dose (4 capsules) will be administered ~30 minutes before breakfast and the evening dose (4 capsules)

will be administered 30 minutes before dinner to cover the luminal bile acid release associated with meals.

The sponsor or designee will provide the investigator and site with additional investigational product information, including dosage form, packaging, storage conditions, and labeling in the Pharmacy Manual. Volixibat may be provided as multiple capsules per dose. The packaged study drug will be labeled in accordance with country and regional specific regulatory requirements, and supplies will be shipped in accordance with the Pharmacy Manual.

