## 6.6. Study Drug Accountability

Study drug will be dispensed at the study visits summarized in the SoA ([Table 1](#)). Returned study drug will not be re-dispensed to participants.

Investigators will be provided with sufficient amounts of the study drug to carry out this protocol for the agreed number of participants. The investigator or designee will acknowledge receipt of the study drug, documenting shipment content and condition. Accurate records of all study drug dispensed, used, returned, and/or destroyed must be maintained.

The investigator has overall responsibility for dispensing study drug. Where permissible, tasks may be delegated to a qualified designee (e.g., a pharmacist) who is adequately trained in the protocol and who works under the direct supervision of the investigator. Study drug will be dispensed at baseline and at each visit in quantities sufficient for dosing at least until the next scheduled visit. If necessary, direct-from-site to participant shipment of study drug is allowed between visits.

The investigator or designee will dispense the study drug only to participants included in this study and following the procedures set out in the study protocol. Each participant will be given only the assigned study drug. All dispensed study drug will be documented in the IRT system.

The investigator is responsible for ensuring the retrieval of all study supplies from participants. Participants must be instructed to bring their unused and empty or used study drug packaging to every visit. Drug accountability must be assessed at the capsule level. The pharmacist or designee will record details on the drug accountability form.

Other than study drug dispensed to participants, no stock or returned inventory may be removed from the site where originally shipped without prior knowledge and written consent by the sponsor. If such transfer is authorized by the sponsor, all applicable local, state, and national laws must be adhered to for the transfer.

The sponsor or its representatives must be permitted access to review the supply storage, distribution procedures, and records provided that the blind of the study is not compromised by such access.

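### The SAP's adherence denominator multiplies a duration expressed in weeks by 2, a multiplier that fits only days; read literally, full adherence comes out at about 700%

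*SAP*

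**What the plan says.** SAP 4.2.1 gives the duration rule: "Total duration of exposure to study drug will be defined as last dosing date minus first dosing date plus 1". The same sentence adds that the result "will be expressed in weeks using up to 1 decimal place". No separate version in days is given. Protocol-specified holds and reductions are named there as an exception to counting straight through interruptions.

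SAP 4.2.2 defines on-treatment adherence as the amount administered divided by the amount expected, times 100. For the denominator, the expected amount "will be derived as 2 x Duration of Exposure to Study Drug", with a pointer back to 4.2.1 and no conversion. For the numerator, "The presumed total number of doses tablets administered to a participant will be determined by the data collected within IXRS for drug accountability"; the displayed formula under that sentence is doses dispensed minus doses returned. The result is summarised for the Safety Analysis Set with descriptive statistics and, as examples, three categories: below 80%, 80% to below 90%, and 90% or more.

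Protocol 6.1 describes twice-daily oral dosing with several capsules each time: "the morning dose (4 capsules) will be administered" before breakfast, and the evening dose is also 4 capsules. Protocol 6.6 adds: "Drug accountability must be assessed at the capsule level".

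**The concern.** The multiplier 2 stands for two doses a day. Applied to a number of weeks, it gives one seventh of the doses due, so the percentage is inflated about sevenfold. On that scale the example cut-offs at 80% and 90% fall far below any level of intake at which one would start to call a participant non-adherent. Nearly everyone would sit in the top category, and the table would carry no information.

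There is a second, separate looseness. SAP 4.2.2 refers to the quantity taken as tablets, as doses, and as both words run together, while the product is a capsule and the protocol's accountability is by capsule. Changing weeks to days does not settle which unit is counted above and below the line.

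**Working it through.** The documents state no adherence figure, so there is nothing to reproduce first. The check applies the stated formula to a participant who takes every dose.

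**Inputs**
- D = last dosing date minus first dosing date plus 1, which is in days (SAP 4.2.1).
- W = D / 7, rounded to 1 decimal (SAP 4.2.1).
- 2 doses per day, so full intake is 2 x D doses (Protocol 6.1).
- Numerator counted in doses, as in the displayed formula (SAP 4.2.2).
- Both doses assumed taken on the first and the last day.

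**As written, duration in weeks:** adherence = 100 x 2D / (2W).

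| D (days) | W (weeks) | Doses taken | 2 x W | Adherence |
|---|---|---|---|---|
| 21 | 3.0 | 42 | 6.0 | 700% |
| 22 | 3.1 | 44 | 6.2 | 709.7% |
| 28 | 4.0 | 56 | 8.0 | 700% |
| 32 | 4.6 | 64 | 9.2 | 695.7% |

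The figure is exactly 700% at whole weeks. Over 21 to 140 days, rounding to one decimal moves it between about 692% and 710%.

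**Where the cut-offs then fall.** Reported adherence is about 7 times true adherence.
- The 80% cut-off corresponds to 80 / 7 = 11.4% of doses truly taken.
- The 90% cut-off corresponds to 90 / 7 = 12.9%.
- A participant taking 13% of her doses reads 7 x 13 = 91%; one taking half reads 7 x 50 = 350%. Both are in the top category.

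**Duration read in days:** 100 x 2D / (2D) = 100% at every duration; at 21 days, 42 / 42.

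**Converting the rounded weeks is not quite enough.** With 14 x W as the denominator, 22 days gives 44 / (14 x 3.1) = 44 / 43.4 = 101.4%. Days, or unrounded weeks, are needed.

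**Counting unit, with duration in days.** At 4 capsules per dose, 21 days of full intake is 42 x 4 = 168 capsules. If capsules were entered above the line and the denominator left at 2 x D, the result would be 168 / 42 = 400%. This is conditional: it arises only if someone substitutes capsules for the doses shown in the displayed formula.

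**The case against.** The best defence is that the unit is not beyond doubt. Subtracting two dates and adding 1 gives days; the weeks clause can be read as a display convention. The exposure bands in 4.2.1 mix a day with weeks, and 4.2.2 ties the expected amount to the regimen, for which a multiplier of 2 makes sense only per day. On that reading the formula gives 100%, and a value near 700% would in any case be noticed at the first programming check. This stands in part. It means that a wrong table is not certain. It does not rescue the text, because 4.2.2 points to a quantity whose only stated unit is weeks.

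Three stronger inferences are tempting, and the documents do not support them.

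- A reader might infer that full adherence would read 168 / 6 = 2800%. That puts capsules into a numerator that the SAP displays in doses. The mixed wording and capsule-level accountability make the unit inconsistent; they do not show that capsules would be used. The SAP also says it is based on protocol Version 1, whose capsule count cannot be seen here.
- A reader might infer that protocol-deviation review would be corrupted, since nonadherence is a listed example of a deviation reason. SAP 4.4 says deviations are documented during routine monitoring, and Protocol 6.7 has its own site check (more than 25% of capsules missed weekly for 2 consecutive weeks). Neither uses the 4.2.2 percentage.
- A reader might infer an effect on the primary estimand. Protocol 10.4.1.1 handles discontinuation for lack of compliance by treatment policy and SAP 6.1.3 lists it under a hypothetical strategy, but the adherence percentage enters neither strategy, nor any model or analysis-set definition.

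**Conclusion.** The point holds as a minor unit error in the SAP text. Followed literally, full adherence reads about 700% (roughly 692% to 710% after rounding, for 21 to 140 days), and anyone above about 13% true adherence falls in the 90%-or-more category, so the table could not show non-adherence. With duration in days, the same formula gives 100%.

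The figures assume a numerator in doses and both doses taken on the first and last day. The inconsistent counting unit is a further drafting fault with no certain numerical effect. The consequence is limited to one descriptive summary on the Safety Analysis Set; the primary analysis, power and Type I error do not change.

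**What to change.** Amend SAP 4.2.2 as follows.

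1. State expected doses = 2 x days of exposure, where days = last dosing date minus first dosing date plus 1, with the handling of holds already in 4.2.1. Keep weeks for display of duration only.
2. Use one counting unit above and below the line: either doses throughout, or capsules dispensed minus returned, converted to doses by the number of capsules dispensed per dose.
3. Delete the word tablets.
4. Say how the stepwise dose reductions permitted in Protocol 6.2 enter the expected amount. The documents do not say whether a reduction changes the number of capsules per dose or their strength, so a capsule-based denominator fixed at the originally assigned dose could misstate adherence after a reduction. Step 2 alone does not settle this.

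The cost is one formula and a few words in the SAP, with no new data collection and no change to any efficacy analysis.
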